7.5.2 Permitted Glucocorticoid Uses

Aside from the required 8-week GC taper (Section 7.2.1), GCs are generally only permitted in this study to treat IgG4-RD flares (see Section 7.6). However, the following are permitted GC use for indications other than IgG4-RD flare:

- Oral GC treatment for ≤ 2 weeks (for any purpose).
- GCs at a dose of ≤ 2.5 mg of prednisone or equivalent for treatment of adrenal insufficiency (mineralocorticoids are permitted) or intolerance of steroid taper (in this case, continued tapering of steroids should be performed as tolerated). GCs at any dose should not be continued for the purpose of prevention of IgG4-RD related flare.
- Inhaled, intranasal or topical corticosteroids.
- Up to 2 intra-articular steroid injections that do not exceed 40 mg methylprednisolone or equivalent per injection.

7.6 Management of Flare of IgG4-RD During the Study

Treatment of flares is at the discretion of the Investigator. Subjects should be managed in accordance with best medical practice for their condition regardless of whether protocol-defined flare criteria are met. Stenting or other procedures are permitted as medically warranted per the judgment of the Investigator. Unless treatment is urgent, in which case medically appropriate therapy should be instituted without delay, Investigators should conduct flare assessments according to the organ(s) affected prior to initiation of treatment, if possible.

Choice of flare treatment is at the discretion of the Investigator. The use of GCs at a dose exceeding 40 mg/day of prednisone or equivalent, or for a duration exceeding 8 weeks including taper to discontinuation, requires discontinuation of IP. Use of any prohibited immunosuppressive treatment for flares requires discontinuation of IP (Section 7.5.1).

8 SAFETY DATA COLLECTION AND REPORTING

An external, independent SDMC will perform evaluations of safety data at specified regular intervals throughout the study and make recommendations to the Sponsor regarding further conduct of the study. See Section 11.1 for details on SDMC activities.

8.1 Definitions

- Adverse event An AE is any untoward medical occurrence associated with the use of an intervention in humans, whether or not it is considered intervention-related.
- Serious adverse event A SAE is considered "serious" if, in the view of either the Investigator or Sponsor, it results in any of the following outcomes:
 - Death
 - A life-threatening AE. (An event is considered "life-threatening" if, in the view of either the Investigator or Sponsor, its occurrence places the patient or subject at immediate risk of death. It does not include an AE or suspected adverse reaction [SAR] that, had it occurred in a more severe form, might have caused death.)
 - Inpatient hospitalization or prolongation of existing hospitalization
 - A persistent or significant incapacity or substantial disruption of the ability to conduct normal life functions
 - A congenital anomaly/birth defect
 - Important medical events that may not result in death, be life-threatening, or require hospitalization may be considered serious when, based upon appropriate medical judgment, they may jeopardize the patient or subject and may require medical or surgical intervention to prevent one of the outcomes listed in this definition. Examples of such medical events include allergic bronchospasm requiring intensive treatment in an emergency room or at home, blood dyscrasias or convulsions that do not result in inpatient hospitalization, or the development of drug dependency or drug abuse.

For the purposes of this protocol, IgG4-RD disease activity or flare that meets any of the above SAE criteria, including hospitalization for a procedure required to manage an IgG4-RD flare, will not be reported as an SAE unless it results in death or occurs during the screening period. Clinically significant events of IgG4-RD disease activity, as determined by the Investigator, should be reported as AEs.

A hospitalization for elective or pre-planned treatment of a pre-existing condition that did not worsen from baseline will not be considered an SAE.

- **Causality or relatedness**: The Investigator is required to provide an assessment of the relationship of AEs and SAEs to the IP. An event will be considered "not related" to use of IP if any of the following tests are met:
 - An unreasonable temporal relationship between administration of the IP and the onset of the event (eg, the event occurred either before, or too long after, administration of the IP for it to be considered IP-related)
 - A causal relationship between the IP and the event is biologically implausible (eg, death as a passenger in an automobile accident)
 - A clearly more likely alternative explanation for the event is present (eg, typical adverse reaction to a concomitant drug and/or typical disease-related event)

Individual AE/SAE reports will be considered "related" to use of the IP if the "not related" criteria are not met.

"Related" implies that the event is considered to be "associated with the use of the drug" meaning that there is "a reasonable possibility" that the event may have been caused by the IP (ie, there are facts, evidence, or arguments to suggest possible causation).

- Adverse reaction An adverse reaction is any AE caused by a drug.
- Suspected adverse reaction A SAR is any AE for which there is a reasonable possibility that the drug caused the AE. For the purposes of safety reporting to regulatory agencies, "reasonable possibility" means there is evidence to suggest a causal relationship between the drug and the AE. SAR implies a lesser degree of certainty about causality than an adverse reaction.
- Unexpected An event is considered unexpected if it is not listed in the IB, is not listed at the specificity or severity that has been observed, or, if an IB is not required or available, is not consistent with the risk information described in the General Investigational Plan or elsewhere. Unexpected also refers to events that are mentioned in the IB as occurring with a class of drugs or as anticipated from the pharmacological properties of the drug but are not specifically mentioned as occurring with the particular IP.
- Severity or intensity Severity will be graded according to the CTCAE, version 5.0. The determination of severity for events not listed in the CTCAE should be made by the Investigator based upon medical judgment and the severity categories of Grade 1 to Grade 5 as defined here, with the maximum severity recorded:
 - Grade 1 (mild): An event of mild intensity that is usually transient and may require only minimal treatment or therapeutic intervention. The event does not generally interfere with usual activities of daily living.
 - Grade 2 (moderate): An event of moderate intensity that is usually alleviated with additional, specific therapeutic intervention. The event interferes with usual activities of daily living, causing discomfort but poses no significant or permanent risk of harm to the subject.
 - Grade 3 (severe): A severe event that requires intensive therapeutic intervention. The event interrupts usual activities of daily living, or significantly affects the clinical status of the subject.
 - Grade 4 (life-threatening): An event, and/or its immediate sequelae, that is associated with an imminent risk of death or with physical or mental disabilities that affect or limit the ability of the subject to perform activities of daily living (eating, ambulation, toileting, etc).
 - Grade 5 (fatal): Death (loss of life) as a result of an event.

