6.4 Discontinuation of Investigational Product, Withdrawal from Study, and Loss to Follow-up

6.4.1 Discontinuation of Investigational Product

IP must be discontinued if the Investigator determines that continuing it would result in a significant safety risk for that subject. The following events require discontinuation of IP:

- 1. Anaphylaxis or a serious hypersensitivity reaction that occurred within 7 days after IV dosing and cannot be attributed to another known allergen exposure (see Appendix B).
- 2. Any AE or significant laboratory abnormality that, in the opinion of the Investigator, Sponsor, or SDMC, warrants discontinuation of dosing.
- 3. Any AE of immune complex disease.
- 4. Any life-threatening (Grade 4) AE.
- 5. Any event of sepsis or febrile neutropenia.
- 6. Any infection listed as either a definite or probable opportunistic infection in Appendix A.
- 7. Any Grade 3 AE with the following exceptions:
 - A Grade 3 AE of flare or exacerbation of IgG4-RD (per protocol, these events are not reported as SAEs as they may represent the primary endpoint of the study)
 - A Grade 3 event that is not an IRR or infection, does not meet any other discontinuation criterion, and for which the SDMC has agreed that IP dosing can continue
- 8. Pregnancy or a decision to become pregnant.
- 9. Malignancy.
- 10. Absolute neutrophil count < 800 cells/µL confirmed by repeat testing.
- 11. Withdrawal of consent for further study participation or for further receipt of IP.
- 12. Receipt of prohibited medication(s) (see Section 7.5.1).
- 13. Determination that the subject was ineligible for study participation and continuation of IP could pose a safety risk to the subject in the judgment of the Investigator or Sponsor.
- 14. Significant noncompliance with the study protocol, as judged by the Investigator or Sponsor.

Severity of AEs will be graded according to the National Cancer Institute Common Terminology Criteria for Adverse Events (CTCAE) (Section 8.1)

Subjects with Grade 3 SAEs should have their AE data reviewed by the Investigator to specifically address whether or not IP should be discontinued or delayed to ensure patient safety, particularly for Grade 3 SAEs of infection (Section 7.1.1.4). The medical monitor(s) and the SDMC are available for discussions regarding suitability of repeat dosing in a subject who has had a Grade 3 SAE.
Clinical Study Protocol	Horizon Therapeutics Ireland DAC
VIB0551.P3.S2 - MITIGATE	Inebilizumab

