#### **3.6.1** Adverse Events

Adverse event and serious adverse event collection begins after the subject signs the informed consent document and continues until the end of study visit. AEs and SAEs collected during the RCP will be analyzed using a treatment policy strategy (which includes all data captured during the RCP), and a while-on-treatment strategy (which includes all data captured while subjects are on treatment). AEs and SAEs collected during the OLP, SFP and combined RCP and OLP, will be analyzed using a treatment policy strategy. For subjects who withdraw from the study, data collected up until the last visit will be included. Table 5 defines TEAEs for different analyses.

RCP (Treatment Policy)	RCP (While-on- treatment)	OLP	Combined RCP and OLP (Any Inebilizumab Analysis Set)	SFP
A TEAE is defined as any AE with onset date on or after the first RCP IP dose, and on or before the end of RCP.	A TEAE is defined as any AE with onset date on or after the first RCP IP dose, and on or before 6 months (183 Days) after the last RCP dose.	A TEAE is defined as any AE with onset date on or after first OLP IP dose and up to the end of OLP (prior to the SFP entry if a subject enrolled into SFP).	A TEAE is defined as any AE with onset date on or after the first inebilizumab dose (either RCP or OLP) and up to and including the day prior to the end of RCP (if a subject didn't enroll into OLP) or the end of OLP (i.e., the day prior to the SFP entry, if a subject rolled over to OLP).	TEAE is defined as any AE with onset date after the last IP dose during the study.

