#### **Table 5 Definition of TEAEs for Different Analyses**

An adverse event of special interest (AESI) is one of scientific and/or medical interest specific to understanding safety and action of the IP. The following are considered AESIs in this study:

- Anaphylaxis and serious hypersensitivity reactions
- Infusion-related reactions (IRR)
- Immune complex disease
- Cytopenia
- Serious and/or opportunistic infections, including Progressive Multifocal Leukoencephalopathy (PML).

The AESIs (investigator reported) will be summarized by Category and PT. The risk difference and corresponding 95% CI calculated by the Miettinen and Nurminen score method in cumulative incidences of AESIs by week 52 between inebilizumab and placebo groups may be presented as appropriate. In addition, the time to first instance of an AESI and duration of the AESI will be summarized by treatment group when appropriate.

In addition, following sponsor identified AESIs will also be summarized: IRR, anaphylaxis, serious hypersensitivity reactions, immune complex disease, cytopenia, serious infections, and opportunistic infections. The detailed definition of sponsor identified AESIs will be included in the statistical programming plan (SPP).

AEs will be coded to the corresponding system organ class (SOC) and preferred terms (PT) using the most recent version of the Medical Dictionary for Regulatory Activities (MedDRA). In addition, summary of AEs and SAEs by SOC and FDA Medical Query (FMQ) will also be provided for RCP and the combined period of RCP and OLP.

The number and percentage of subjects reporting TEAEs and TESAEs will be summarized for each treatment group by SOC and PT, by severity, and by relationship to the IP. If the same AE occurs multiple times within a particular subject, the highest severity and level of relationship observed will be reported.

TEAEs and TESAEs will be summarized as described in Table 6.

TEAEs per 100 Person-years for a specific reporting period will be calculated as

$$= 100 \times \frac{\text{Total number of TEAEs for specific reporting period}}{\text{Total Person years for specific reporting period}}$$

The person-year for while-on-treatment analyses will be defined as (Date of 6 months [183 Days] after the last RCP dose - 1st RCP dose date +1)/365.25. See Table 4 for the definition of person-years for other analyses.

Overall summary of TEAEs
TEAEs by SOC and PT
TEAEs with severity $\geq$ Grade 3 by SOC and PT

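### All-TEAE totals, Grade 3 or higher tables and per-100-person-year rates include IgG4-RD flares, so they tilt towards inebilizumab if it works as planned; versions without flares should stand beside them

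*Protocol*

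**What the plan says.** Protocol Section 8.1 treats disease activity differently for SAEs and AEs. Activity or flare that meets a seriousness criterion "will not be reported as an SAE unless it results in death or occurs during the screening period". The same paragraph adds that "Clinically significant events of IgG4-RD disease activity, as determined by the Investigator, should be reported as AEs". Protocol Section 6.4.1 expects such AEs to reach higher grades: its list of exceptions includes "A Grade 3 AE of flare or exacerbation of IgG4-RD", and it explains that flares are kept out of SAE reporting because they may be the primary endpoint.

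The SAP makes no matching provision for AEs. For the RCP, Table 5 says "A TEAE is defined as any AE with onset date on or after the first RCP IP dose". The text of SAP Section 3.6.1 continues: "The number and percentage of subjects reporting TEAEs and TESAEs will be summarized for each treatment group by SOC and PT". Table 6 lists an "Overall summary of TEAEs" and a table of TEAEs at or above "Grade 3 by SOC and PT". The rate per 100 person-years has as its numerator the "Total number of TEAEs for specific reporting period".

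Neither document removes IgG4-RD activity from these tables, shows it on its own line, or gives a rule for grouping flare terms that are coded to different organs. TEAE incidence is a secondary endpoint (Protocol Section 3.2), and Protocol Section 9.5.5 plans a risk difference with a 95% CI for AEs collected in the RCP.

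**The concern.** The trial is designed on the expectation that flares will be much less frequent on inebilizumab. If flares also enter the AE counts, an effective drug lowers its own AE total by being effective. A comparison meant to show harm then partly restates benefit. The consequence that matters is masking: an excess of non-flare events on inebilizumab could be offset by fewer flares, leaving the any-TEAE percentage, the Grade 3 or higher percentage or the event rate level between arms. The protocol recognises this overlap for SAEs and deals with it there, but not for AEs.

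**Working it through.** **Inputs from the plan** (Protocol Sections 9.2 and 9.3; SAP Section 2.3): placebo flare probability 0.35, HR 0.35, 39 flares, 90% power, two-sided alpha 0.05, 80 subjects per arm.

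**Reproducing the plan's figures.** The Schoenfeld formula gives 39 events, with power 90.6%. The hazards are −ln(0.65) = 0.4308 and 0.35 × 0.4308 = 0.1508. The inebilizumab flare probability is 1 − exp(−0.1508) = 0.140. Pr(Fail) = (0.35 + 0.14)/2 = 0.245, and 39/0.245 = 159.2, so N = 160. The expected split is 80 × 0.35 = 28 placebo subjects with a flare and 80 × 0.14 = 11.2 on inebilizumab.

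**Assumptions that the documents do not supply.** Non-flare AE risk q is equal in both arms and independent of flare, and every treated, AC-determined flare is reported as an AE. Any-TEAE incidence is then 1 − (1 − q)(1 − p), and the gap between arms is (1 − q) × 0.21.

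**Background risk.** The only figure in the documents is 71.8% versus 73.2% in the NMOSD study (Protocol Section 2.1.5.3), over a 28-week period. This RCP lasts 52 weeks. Under a constant hazard, 72% at 28 weeks becomes 1 − 0.28^(52/28), about 91%.

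| Background q | Placebo | Inebilizumab | Difference (points) |
|---|---|---|---|
| 50% | 67.5% | 57.0% | −10.5 |
| 71.8% | 81.7% | 75.7% | −5.9 |
| 80% | 87.0% | 82.8% | −4.2 |
| 90% | 93.5% | 91.4% | −2.1 |

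The last row is closest to the NMOSD figure carried to 52 weeks. The 50% row has no support in the documents and is shown only for range.

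**Partial reporting.** If 25% to 75% of flares become AEs, the gap at 71.8% background is 1.5 to 4.4 points. At 90% background it is 0.10 × 0.25 × 0.21 = 0.5 points to 0.10 × 0.75 × 0.21 = 1.6 points.

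**Masking.** The inebilizumab non-flare risk that would make the totals equal is 1 − (1 − q) × 0.65/0.86. At q = 71.8% this is 78.7%, so an excess of 6.9 points would show as no difference. At q = 90% it is 1 − 0.10 × 0.65/0.86 = 92.4%, an excess of 2.4 points.

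**Rates.** SAP Table 4 counts person-years from first dose to the last RCP day, about one year per completer, and does not stop at the flare. First flares therefore add roughly 35 versus 14 events per 100 person-years, a gap of 21; repeat flares would add more. (The hazards of 43 versus 15 per 100 person-years at risk use a different denominator.) With an assumed equal background of 100 per 100 person-years, a true rate ratio of 1.00 would show as 114/135 = 0.84; with 300, as 314/335 = 0.94; with 500, as 514/535 = 0.96.

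**Grade 3 or higher.** The share of flares at this grade is unknown. With an assumed 10% background and 25% of flares at Grade 3 or above: placebo 1 − 0.90 × (1 − 0.25 × 0.35) = 17.9%; inebilizumab 1 − 0.90 × (1 − 0.25 × 0.14) = 13.2%; a gap of 4.7 points. Over backgrounds of 5% to 20% and shares of 10% to 50%, the gap runs from 1.7 to 10.0 points.

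**The case against.** The strongest reply is that the safety assessment does not rest on these totals. SAEs exclude flares with narrow exceptions. The AESI categories in Protocol Section 8.4 contain no flare category, and the SAP attaches its risk difference to AESIs. Protocol Section 8.1 makes a typical disease-related event a ground for judging an AE unrelated, so the IP-related tables, including those at Grade 3 or higher, largely screen flares out. TEAEs are also shown by SOC and PT, by PT frequency and by FMQ, with full listings, so a specific toxicity could be seen even if the total were level. No test or decision rule depends on total TEAE incidence. All of this stands, and it limits the point to the all-TEAE totals.

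It does not remove the point. The IP-related tables depend on investigator causality and also drop non-flare events judged unrelated. The SOC and PT tables show flare terms only in scattered form: flare criteria in Protocol Appendix D are organ-specific, liver and kidney flares rest partly on laboratory findings, and clinically important laboratory abnormalities are themselves recorded as AEs (Protocol Section 6.3.3). A reader cannot reliably subtract them from a total.

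On size, the objection is right that the tilt is probably modest. Only flares the investigator considers clinically significant become AEs, and the background over 52 weeks may be near 90%. Even the 5.9-point gap lies inside sampling error: with 80 per arm the 95% half-width is 1.96 × √(0.8167 × 0.1833/80 + 0.7575 × 0.2425/80), about 12.7 points. But sampling error has no preferred direction, whereas this shift does.

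A reader might go further and infer that the planned safety analysis as a whole will make inebilizumab look safer, or that conclusions should be drawn only from tables without flares. The documents support neither. The tilt needs a flare reduction not yet shown; with no effect on flares there is none. Removing events by a bare term list could also delete genuine hepatic or renal drug events.

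**Conclusion.** The point holds for three outputs: the overall TEAE summary, the Grade 3 or higher TEAE table and the TEAE rates per 100 person-years. They include part of the efficacy outcome, and under the plan's own effect (35% versus 14%) they favour inebilizumab and can hide a non-flare excess. The any-TEAE tilt is about 2 points at a 90% background and about 6 at 72%, given equal, independent non-flare risk and full reporting of flares as AEs; partial reporting shrinks it in proportion. First flares add roughly 35 versus 14 events per 100 person-years of full RCP time. The effect on Grade 3 or higher events cannot be sized without knowing how many flares reach that grade. Overlap with the primary endpoint is not exact, because AE reporting follows investigator judgement and the endpoint requires treatment and adjudication. SAE, AESI and IP-related tables are largely unaffected. This is a small but directional and avoidable weakness in presentation, not a flaw in the safety analysis as a whole.

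**What to change.** In SAP Table 6, add beside the all-TEAE versions a second set of the overall summary, the Grade 3 or higher table and the per-100-person-year tables. This set should exclude AEs that meet both conditions: the investigator identifies the event as IgG4-RD activity, and it is linked to an event on the flare eCRF. Appendix D already has organ-level findings recorded for each potential flare, including those that do not meet criteria, so the link needs no new clinical assessment. If the eCRF has no linking field, the matching rule should be written out. Fix the rule before unblinding, and state that the between-arm comparison will be interpreted from both sets.

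The cost is a few more tables and the linkage work. The downside is a small risk that a drug event is misattributed to flare and left out of the second set; keeping the all-TEAE tables covers that. Sample size, endpoints and trial conduct do not change.

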8.2 Documenting Adverse Events

AEs reported by the subject, spontaneously or in response to an open question from the study personnel, and AEs revealed by observation will be recorded during the study at the investigational site. For each AE, the Investigator will evaluate and report the onset (date and time), resolution (date and time), severity, causality, action taken, serious outcome (if

applicable), and whether or not it caused the subject to discontinue the study. The AE term should be reported in standard medical terminology when possible.

8.3 Reporting Adverse Events

All AEs (related and unrelated) will be recorded from written ICF signature up to exit from the study, whether or not related to the study.

In addition to eCRF entry, all SAEs must be reported to the Sponsor within 24 hours of site staff awareness by submitting a SAE Report Form by email to:

Email: [contact]

Alternatively, the SAE Report Form can be submitted by fax to:

US-Only [contact]

EX-US [contact]

Additional follow-up information, if required or available, should all be reported within one business day of receipt, should be completed on a follow-up SAE form, placed with the original SAE information, and kept with the appropriate section of the eCRF and/or study file.

The Sponsor will work with the Investigator to ensure that all the necessary information is provided within one calendar day of initial receipt for fatal and life threatening events and within 5 calendar days of initial receipt for all other SAEs.

Sponsor or designee is responsible for notifying the relevant regulatory authorities of certain events. Notification of the IRB or IEC of all SAEs that occur at the Investigator's site are the responsibility of the Investigator. Investigators will be notified of all unexpected, serious, drug -related events (7 and 15 Day Safety Reports) that occur at other investigative sites during the clinical trial. Each Investigator is responsible for notifying its IRB or IEC of these additional SAEs.

